## **7. INVESTIGATOR REQUIREMENTS**

### **7.1 RETENTION OF RECORDS**

FDA regulations (21 CFR §312.62[c]) and the International Council for Harmonisation (ICH) Guideline for GCP (see Section 4.9 of the guideline) require that records and documents pertaining to the conduct of clinical trials and the distribution of investigational drug, patient records, consent forms, laboratory test results, and medication inventory records, must be retained for 2 years after the last marketing application approval in an ICH region or after at least 2 years have elapsed since formal discontinuation of clinical development of the investigational product. All state and local laws for retention of records also apply.

For studies conducted outside the U.S. under a U.S. IND, the Principal Investigator must comply with the record retention requirements set forth in the FDA IND regulations and the relevant national and local health authorities, whichever is longer.

### **7.2 STUDY MEDICAL MONITORING REQUIREMENTS**

This clinical research study will be monitored both internally by the PI and externally by the WCG IRB. In terms of internal review, the PI will continuously monitor and tabulate AEs. Appropriate reporting to the WCG IRB will be made. The PI of this study will also continuously monitor the conduct, data, and safety of this study to ensure that:

- Interim analyses occur as scheduled,
- Stopping rules for toxicity and/or response are met,
- Risk/benefit ratio is not altered to the detriment of the subjects,
- Appropriate internal monitoring of AEs and outcomes is done,
- Over-accrual does not occur,
- Under-accrual is addressed with appropriate amendments or actions, and
- Data are being appropriately collected in a reasonably timely manner.

Routine monitoring will be carried out via a periodic team conference among investigators during which toxicity data, including all SAEs, will be reviewed and other issues relevant to the study such as interim assessment of accrual, outcome, and compliance with study guidelines, will be discussed. Monitoring will be carried out on an ongoing basis. The severity, relatedness, and whether or not the event is expected will be reviewed.

### **7.3 DATA COLLECTION**

The study coordinator and investigators are responsible for ensuring that the eligibility checklist is completed in a legible and timely manner for every patient enrolled in the study, and that data are recorded on the appropriate forms and in a timely manner. Any errors on source data should be lined through, but not obliterated, with the correction

inserted, initialed, and dated by the study coordinator or PI. All source documents will be available for inspection by the FDA and the WCG IRB.

## **8. ETHICAL CONSIDERATIONS**

### **8.1 COMPLIANCE WITH LAWS AND REGULATIONS**

Patients who comply with the requirements of the protocol, are tolerating study treatment, and may be receiving benefit will be offered dosing beyond Cycle 1 at the investigator's discretion after a careful assessment and thorough discussion of the potential risks and benefits of continued treatment with the patient. Such patients may have the option to receive Xofluza treatment as long as they continue to experience clinical benefit in the opinion of the investigator until the earlier of unacceptable toxicity, symptomatic deterioration attributed to disease progression, or any of the other reasons for treatment discontinuation listed in [Section 4.6](#).

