COVID-19 and influenza testing unit to communities where individuals already gather for other social events provides increased access to testing addresses many of these challenges that are experienced in underserved and socially vulnerable communities. However, identification and testing of individuals who may reside in hot spots for respiratory viruses is not sufficient to completely mitigate the spread of disease or reduce the effects of infection. Rapid access to effective therapeutics within the narrow antiviral therapeutic window (48 hours from symptom onset) is necessary to reduce the spread of infection and reduce disease severity.

In this study will use our Respiratory Infection Hot Spot Algorithm that identifies and supports deployment of mobile testing units to community centers, parks and senior centers in socially and economically disadvantaged communities to deploy a mobile test-to-treat model for Influenza A&B, along with testing for SARS-CoV-2 in socially vulnerable communities. Use of a point care test (POCT) for Influenza A&B and SARS-CoV-2 and a mobile pharmacist model enables the test-to-treat model that will target vulnerable communities that may lack access to testing and/or providers for treatment for influenza.

Xofluza is a first-in-class influenza antiviral that blocks RNA replication by inhibiting cap-dependent endonuclease activity (Omoto et al. 2018). Xofluza is administered by a convenient and unique one-dose, one-time regimen. In the Phase III CAPSTONE-1 double-blind randomized study in otherwise healthy patients (Hayden et al. 2018), a single treatment of Xofluza (40 mg for patients < 80 kg and 80 mg for patients  $\geq$  80 kg) significantly reduced the time to alleviation of symptoms compared with placebo and also effectively reduce viral load, as shown by a significant reduction compared with placebo in:

- The proportion of patients with positive influenza titer between Days 2 and 5
- The proportion with positive influenza virus RNA determined by PCR on Day 5
- The median time to cessation of viral shedding

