Using a longitudinal patient database with an active system to prospectively geocode addresses entered into our system, we are able to determine, at the census tract level, neighborhoods that are at high risk for viral transmission because they are a hot spot or testing desert. We are then able to incorporate the social vulnerability index as an additional weighted measure to the hot spot or desert score in order to calculate an identified hot spot or desert risk for a census tract. Through collaboration with local community centers, we are able to deploy a mobile testing unit to a community center, park or senior center that is in close proximity to the identified neighborhood for rapid onsite testing for Influenza A&B and SARS-CoV2 using the cobas Liat system.

New Mexico has adopted “New Mexico Board of Pharmacy Protocol for Pharmacists Prescribing of Dangerous Drugs in Conjunction with Point of Care Testing” (NMBOP POCT Protocol, Appendix 5) that allows pharmacists the prescriptive authority to prescribe Influenza antiviral therapy in conjunction with a positive point of care test (POCT). TriCore employs two (2) on-site clinical pharmacists who will follow all of the pharmacist mandates included in the regulation to prescribe and distribute Xofluza according to the approved protocol in the test-to-treat model presented in this study. The NMBOP PCOT Protocol documents the eligibility and requirements of the certified prescribing pharmacists (pharmacist) following this protocol.

The pharmacist will perform a screening physical assessment, health assessment and medical history for the patient. If the subject meets the inclusion criteria, they will have a point of care test performed. If the subject meets the exclusion criteria, they will be excluded from the study. Testing will be performed using the cobas® SARS-CoV-2 & Influenza A/B assay on the cobas® Liat® system from a self-collected nasal swab. Subjects who test positive for influenza A or B will be prescribed Xofluza with no additional refills. The pharmacist will follow-up with the patient 24-48 hours following administration for evaluation of

signs/symptoms and will refer the patient to their primary care provider, provider, or clinic for recommended laboratory testing and follow-up if appropriate.

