#### Description of Xofluza treatment schedule:

Xofluza will be administered as a single oral dose as soon as possible and within 48-hours of influenza symptom onset. Dosing will be delivered based on the package insert.:

Patient Body Weight (kg)	Recommended Single Oral Dose in Patients 5 years of Age and Older (Tablets)
20 kg to less than 80 kg	One 40 mg tablet (blister card contains one 40 mg tablet)
At least 80 kg	One 80 mg tablet (blister card contains one 80 mg tablet)

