### **3.2 END OF STUDY AND LENGTH OF STUDY**

The end of this study is defined as the date when 12 weeks of mobile testing and treating deployment has concluded or the end of “influenza season” as defined by the New Mexico Department of Health, whichever is last. As this is a single dose observational study, there are no follow-up visits scheduled as part of the study. All subjects receiving the therapeutic will receive a follow-up phone call 24-48 hours following administration of Xofluza. All enrolled subjects will receive a follow-up phone call 14-days following the initial screening visit to assess symptom resolution and socioeconomic impact of their test result. The end of the study is expected to occur 12 months after the last patient is enrolled to allow for complete data analysis and evaluation. In addition, the Investigator may decide to terminate the study at any time.

The total length of the study, from screening of the first patient to the end of the study, is expected to be approximately 15 months.

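### Section 8.1 permits Xofluza dosing beyond a first cycle with no maximum number of doses, which contradicts the single-dose regimen in Sections 3.1 and 3.2

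*Combined protocol and SAP*

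**What the plan says.** Four statements fix a single dose:

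- Section 1.3: "Xofluza is administered by a convenient and unique one-dose, one-time regimen".
- Section 3.1, main text: "Subjects who test positive for influenza A or B will be prescribed Xofluza with no additional refills".
- Section 3.1, treatment schedule: "Xofluza will be administered as a single oral dose as soon as possible and within 48-hours of influenza symptom onset".
- Section 3.2: "As this is a single dose observational study, there are no follow-up visits scheduled as part of the study". Contact after the visit is by telephone: "All subjects receiving the therapeutic will receive a follow-up phone call 24-48 hours following administration of Xofluza", and "All enrolled subjects will receive a follow-up phone call 14-days following the initial screening visit".

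Section 8.1 is headed as a statement of compliance with laws and regulations but contains a dosing paragraph. Patients who follow the protocol, tolerate treatment and may be benefiting "will be offered dosing beyond Cycle 1", subject to the investigator's judgement and a discussion of risks and benefits. They may then receive Xofluza "as long as they continue to experience clinical benefit in the opinion of the investigator". Treatment ends at unacceptable toxicity, symptomatic deterioration put down to disease progression, or another reason listed in Section 4.6, whichever comes first.

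**The concern.** How many doses of study drug a patient may receive is a basic protocol instruction, and here it has two incompatible answers. The protocol gives no rule for which section prevails. A site or ethics committee that reads Section 8.1 on its own would conclude that repeat dosing is approved, with the investigator's view of benefit as the main control. Such doses would lie outside the regimen that the study describes and, in most cases, outside the 48-hour treatment window. The issue concerns treatment instructions and does not touch the sample size or the analysis of hot spot scores.

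**Working it through.** The plan has no computed figure to reproduce here, so the check sets the texts side by side.

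| Feature | Sections 1.3, 3.1 and 3.2 | Section 8.1 |
|---|---|---|
| Doses per treated patient | Exactly 1 | 1 or more, no upper limit stated |
| Refills | None (Section 3.1 only) | Further treatment left open |
| Timing | Within 48 hours of onset (Section 3.1) | No limit |
| Later visits | None; telephone calls only (Section 3.2) | Benefit and tolerability must be judged again, but no visit is provided |
| End of treatment | The one dose has been taken | Toxicity, deterioration or a Section 4.6 reason |

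**Can the two columns be reconciled?** Only if a cycle had a meaning under which nothing follows the first. The protocol defines no cycle, dosing interval or redosing visit.

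**Does Section 4.6 supply a cap?** No. Its list consists of clinical and investigator-judged reasons, and completing the single dose is not among them. Its item on loss of benefit refers the reader to Section 3.1.1, but the contents list and the body go from Section 3.1 straight to Section 3.2.

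**Does Section 5.1.2 settle it?** No. Section 5.1.2.1 bars dose modification, which does not address the number of doses. Section 5.1.2.2 directs discontinuation by reference to Section 4.1.2, which holds the entry exclusions. The discontinuation list is in Section 4.6.

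**Timing.** Let the first dose be given h hours after onset, with h between 0 and 48, and a second dose t hours later. The second dose meets the Section 3.1 limit only if h + t ≤ 48, that is t ≤ 48 − h. Since h is at least 0, any dose more than 48 hours after the first is outside the window for every patient.

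**Reach.** The Section 6.1 table prints 54–180 treated patients. The lower end follows from its inputs (60 × 0.90 = 54). The upper end does not (240 × 0.90 = 216), and the text of the same section expects about 430. The share of treated patients who would meet the Section 8.1 conditions is not given. No number of affected patients can therefore be stated.

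**The case against.** The best defence is that every section that actually governs treatment points to one dose. Section 8.1 sits in the ethics chapter under an unrelated heading and speaks of cycles and disease progression, which have no place in a study of acute influenza. The case report form in Appendix 1 has a prescription box and no redosing field, and no visit exists at which to redose. On this view it is leftover template text that nobody would follow. Most of this stands: the origin is an inference, but a reasonable one, and the likelihood of repeat dosing is low. It explains the paragraph without removing it, because the text is current, names Xofluza and links to this protocol's own Section 4.6.

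Some stronger readings are tempting, and the documents do not support them.

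- *Repeat dosing is planned.* Nothing outside Section 8.1 provides for it. The phrases in Sections 4.5 and 4.5.4 that refer to each dose or treatment do not authorise a second one.
- *Safety follow-up would break down.* If the 48-hour limit is kept, two doses are at most two days apart. With the first dose on the screening day, the 14-day reporting period would then outlast the day-14 call by at most two days. Without the limit, no interval is given and no gap can be stated. Events that patients volunteer are reportable (Section 5.3.2), and serious events attributed to treatment stay reportable afterwards (Sections 5.3.1 and 5.4.2.10).
- *Section 5.1.2.2 obliges every patient to stop after the first dose, because Section 4.1.2 excludes prior Xofluza.* That exclusion applies to study entry. The reference is simply to the wrong section.
- *The protocol has no compliance statement.* Section 8.3 carries a one-sentence version.

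**Conclusion.** The contradiction is real and should be corrected. Sections 3.1 and 3.2 give exactly one dose per treated patient. Section 8.1 gives one or more, with clinical stopping criteria and investigator discretion but no stated maximum. Followed as written, Section 8.1 would permit doses outside the planned regimen and the 48-hour window, so this goes beyond a clerical slip. It is an internal inconsistency with a low chance of being acted on. No effect on sample size, schedule or analysis is claimed.

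The conclusion rests on the current text alone and needs no numerical assumption. That the paragraph is carried-over template wording is an inference, and the verdict does not depend on it.

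**What to change.** 1. Delete the dosing paragraph in Section 8.1 and replace it with the statement of compliance with laws and regulations that the heading announces.
2. State in Section 4.3.2 that each patient receives one dose of Xofluza only.
3. As related clean-up, correct the reference in Section 5.1.2.2 from Section 4.1.2 to Section 4.6.
4. Remove from Section 4.6 the item on loss of benefit, with its pointer to the non-existent Section 3.1.1.

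The cost is amendment wording, with the change reported to the IRB as Section 8.3 requires. Sample size, visit schedule and analysis stay as they are.

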### **8.2 INFORMED CONSENT**

The informed consent document must be signed by the subject or the subject's legally authorized representative before his or her participation in the study. The case history for each subject shall document that informed consent was obtained prior to participation in the study. A copy of the informed consent document must be provided to the subject or the subject's legally authorized representative. If applicable, it will be provided in a certified translation of the local language.

Signed consent forms must remain in each subject's study file and must be available for verification by study monitors at any time.

### **8.3 INSTITUTIONAL REVIEW BOARD OR ETHICS COMMITTEE**

This protocol, the informed consent document, and relevant supporting information must be submitted to the IRB for review and must be approved before the study is initiated. The study will be conducted in accordance with FDA, applicable national and local health authorities, and IRB requirements.

The Principal Investigator is responsible for keeping the IRB apprised of the progress of the study and of any changes made to the protocol as deemed appropriate, but in any case, the IRB must be updated at least once a year. The Principal Investigator must also keep the IRB informed of any significant AEs.

Investigators are required to promptly notify their respective IRB of all adverse drug reactions that are both serious and unexpected. This generally refers to SAEs that are not already identified in the Investigator's Brochure and that are considered possibly or probably related to the molecule or study drug by the investigator. Some IRBs may have other specific AE requirements to which investigators are expected to adhere.

Investigators must immediately forward to their IRB any written safety report or update

provided by Genentech (e.g., IND safety report, Investigator's Brochure, safety amendments and updates, etc.).

#### **8.4 CONFIDENTIALITY**

Patient medical information obtained by this study is confidential and may be disclosed to third parties only as permitted by the ICF (or separate authorization to use and disclose personal health information) signed by the patient or unless permitted or required by law.

Medical information may be given to a patient's personal physician or other appropriate medical personnel responsible for the patient's welfare for treatment purposes.

Data generated by this study must be available for inspection upon request by representatives of the FDA and other regulatory agencies, national and local health authorities, Genentech representatives and collaborators, and the IRB/Ethics Committee (EC) for each study site, if appropriate.

### Study Flowchart

## Appendix 1: Study Flowchart

---

### **Patient Case Report Form**

Study Number: \_\_\_\_\_ Patient DOB: \_\_\_\_\_

#### ENROLLMENT INFORMATION:

Informed Consent and assent form completed: \_\_\_ YES \_\_\_ No

Conforms with Inclusion and Exclusion Criteria: \_\_\_ YES \_\_\_ No

**MUST HAVE CONSENT AND PATIENT MUST MEET CRITERIA TO CONTINUE**

Physical assessment and medical history documented

\_\_\_ YES \_\_\_ No

#### TESTING:

Cobas Liat SARS-CoV2 and Influenza A&B Test Result:

	Result	Action Taken
SARS CoV 2		 Patient counseling  Provider referral
Influenza A		 Prescription provided  Patient counseling  Provider referral
Influenza B		

#### VISIT COMPLETION

Survey returned: \_\_\_ YES \_\_\_ No

## Appendix 1: Study Flowchart

### 14- Day Follow-Up Survey

Subject Number: \_\_\_\_\_

Did anyone else in your household test positive at the testing event:

Influenza:  YES  No COVID:  YES  No

Did anyone else in your household test positive for influenza or COVID following the testing event:

Influenza:  YES  No COVID:  YES  No

Did anyone else in your household have any of the symptoms above following the testing event?  YES  No

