## **2. OBJECTIVES AND ENDPOINTS**

### **2.1 PRIMARY OBJECTIVE(S)**

This study seeks to demonstrate that the laboratory can mitigate respiratory virus transmission in underserved populations by using laboratory data to identify communities at risk for increase vial activity (hot spots) and intervening with a test-to-treat model provides increased access to influenza diagnostics and treatment in vulnerable and underserved communities.

1. The hot-spot frequency and hot spot score trend will be measured for each census tract to determine if the screen and treat intervention has an impact on reducing hot spot identification or hot spot score.
  - a. Following each mobile intervention, we will evaluate the hot spot score for the census tracts receiving a mobile screen and treat intervention and SVI-matched census tract not receiving an intervention for 14-days following the screen and treat intervention.
  - b. Patients will receive a follow-up phone call 14-days following their initial screening visit to assess patient and household symptoms and the socioeconomic impact of their test result and treatment access.

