All subjects eligible for Xofluza will receive patient education and counseling on drug information, adherence, side effects, and other patient educational materials, as appropriate. All subjects eligible for influenza antiviral therapy, but having contraindications to the therapy, or do not wish to use the therapy will be referred to their primary care provider, provider, or clinic for further evaluation.

Subjects testing positive for SARS-CoV-2 will be preferred by the pharmacist to the subjects' primary care provider, provider, or clinic for further medical assessment and follow-up, if appropriate. Subjects testing negative for all targets (SARS-CoV-2 and Influenza A&B) with a high index of suspicion for influenza, will be referred by the pharmacist to the subjects' primary care provider, provider, or clinic for further medical assessment and follow-up, if appropriate. All subjects will receive a follow-up call 14-days following the study visit to assess their symptom resolution and the impact of their illness on their well-being (Appendix 1).

The mobile testing unit will be deployed a minimum of 2 times per week following the determination of the influenza season by the New Mexico Department of Health. We expect to screen 50-100 patients per week for the duration of the influenza season (approximately 12 weeks) for a total of 600-1,2000 patients. With an anticipated 10% positivity rate for influenza, we expect at least 5-10 patients per week to be eligible for treatment for a total of 60-120 subjects eligible over the course of the study. All subjects will be provided a survey to evaluated their ability to access respiratory virus testing and their acceptance of and trust in using a mobile unit for access to treatment and therapeutics. Patients positive for SARS-CoV-2 will be counseled on options for treatment and follow up for COVID-19 infection. All subjects enrolled in the study will receive a follow-up phone call 14-days following the initial screening visit.

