#### **3.3.2 Rationale for Patient Population**

As described above, treatment with Xofluza has been shown to reduce viral load and symptoms in patients with influenza A or B. Therefore, this study was designed to see if a test and treat model would have significant impact on community transmission in socially vulnerable communities.

The inclusion criteria limit index patients to those with symptom onset within 48 hours. This is because it is believed that Xofluza will be most effective at preventing viral transmission if given early in the course of infection. (This 48-hour period is also consistent with the labels approved to date for Xofluza in countries including the US, Hong Kong, and Japan).

The study eligibility criteria allow for the inclusion of index patients who are minors. This is also consistent with the labels approved to date for baloxavir marboxil, which is approved for use in individuals aged  $\geq 5$  years of age.

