#### **4.1.2 Exclusion Criteria**

Patients who meet any of the following criteria will be excluded from study entry:

- Patients who have received more than 48 hours of antiviral treatment for the current influenza infection prior to screening
- Patients who have received Xofluza for the current influenza infection
- Known contraindication to neuraminidase inhibitors
- Patients weighing  $< 20$  kg
- Patients unable to swallow tablets
- Patients with known severe renal impairment (estimated glomerular filtration rate  $< 30$  mL/min/1.73 m $^2$ ) or receiving continuous renal replacement therapy, hemodialysis, peritoneal dialysis
- Patients with any of the following laboratory abnormalities detected within 24 hours prior to or during screening (according to local laboratory reference ranges:
  - ALT or AST level  $> 5$  times the upper limit of normal (ULN)  
OR
  - ALT or AST  $> 3$  times the ULN and total bilirubin level  $> 2$  times the ULN
- Pregnant or breastfeeding, or positive pregnancy test in a predose examination, or intending to become pregnant during the study or within 28 days after the last dose of study treatment
- Exposure to an investigational drug within 5 half-lives or 30 days (whichever is longer) of randomization
- Any serious medical condition or abnormality in clinical laboratory tests that, in the investigator's judgment, precludes the patient's safe participation in and completion of the study
- Known hypersensitivity to Xofluza (baloxavir marboxil) or the drug product excipients

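### Several members of one household can enrol and each answers the household survey items, but neither form has a household identifier and the symptom item does not require new onset

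*Combined protocol and SAP*

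**What the plan says.** Objective 1b, placed under the primary objective in Section 2.1, uses the 14-day call to "assess patient and household symptoms and the socioeconomic impact of their test result and treatment access". Section 3.1 states who is called: "All subjects enrolled in the study will receive a follow-up phone call 14-days following the initial screening visit".

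The survey in Appendix 1 has three yes/no household items, the first two split by influenza and COVID:

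- Item 1: "Did anyone else in your household test positive at the testing event"
- Item 2: "Did anyone else in your household test positive for influenza or COVID following the testing event"
- Item 3: "Did anyone else in your household have any of the symptoms above following the testing event"

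A grid then records activities missed by the respondent or by household members, with the days missed.

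Neither Section 4.1.1 nor Section 4.1.2 mentions households. Section 3.3.2 uses the language of a household study ("The inclusion criteria limit index patients to those with symptom onset within 48 hours"), but no rule names one index patient per home. The case report form identifies a subject by study number and date of birth, and the survey by subject number. Section 6.5 describes only the tract hot spot score. It gives no unit of analysis, de-duplication rule or clustering rule for the household items.

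**The concern.** Item 1 makes sense only if members of one home may be tested at the same event. Those members can all enrol, and each then answers the same questions about the same home. Once the forms are filed, nothing recorded on them shows which came from one address.

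Two things are at stake. First, a tally of yes answers is not a tally of affected homes, and repeated reports of one event look like separate pieces of evidence. Second, item 3 can mix two different things. A co-enrolled member has been symptomatic for 48 hours or less at entry, as Section 4.1.1 requires. If that person is still coughing the next day, a sibling can truthfully answer yes to item 3 although nobody has newly fallen ill. For a measure meant to describe household illness after a test-to-treat visit, that is a problem of content as well as precision.

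**Working it through.** **Inputs from the documents.** 50 to 100 patients a week for about 12 weeks (Sections 3.1 and 6.1), all receiving the 14-day call. 50 × 12 = 600 and 100 × 12 = 1,200, which reproduces the 600–1,200 of Section 4.1. The documents give no number of enrollees per household (*m*), no within-household correlation (ICC) and no household illness rate. All three are assumptions below.

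**Repeated yes answers.** In a home with *m* enrolled members:

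- one later case in a non-enrolled member gives *m* yes answers (2, 3 or 4 for *m* = 2, 3 or 4);
- one later case in an enrolled member gives *m* − 1;
- if all *m* ≥ 2 enrolled members are positive at the event, item 1 gives *m*.

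**Apparent precision.** Design effect = 1 + (*m* − 1) × ICC; effective number = surveys / design effect.

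| Mean *m* | ICC | Design effect | Effective number from 600–1,200 |
|---|---|---|---|
| 1.25 | 1 | 1.25 | 480–960 |
| 1.5 | 1 | 1.5 | 400–800 |
| 2 | 1 | 2 | 300–600 |
| 1.5 | 0.5 | 1.25 | 480–960 |

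**Item 2, share reporting a later positive.** Assume 70% of homes enrol one member and 30% enrol three, so there are 0.7 + 0.9 = 1.6 subjects per home.

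- Rates of 15% in single-enrollee and 40% in three-enrollee homes. Per household: 0.7 × 0.15 + 0.3 × 0.40 = 22.5%. Per subject: (0.7 × 0.15 + 0.9 × 0.40) / 1.6 = 0.465 / 1.6 = 29.1%, about 29% too high in relative terms.
- Rates swapped. Per household: 0.7 × 0.40 + 0.3 × 0.15 = 32.5%. Per subject: (0.7 × 0.40 + 0.9 × 0.15) / 1.6 = 0.415 / 1.6 = 25.9%, about 20% too low.
- Equal rates: the two shares are identical.

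Equal rates still leave the count inflated. Take 100 homes, 20 of them enrolling three members, and a later case in 20% of homes of each kind. There are 80 + 60 = 140 subjects and 80 × 0.2 + 60 × 0.2 = 28 yes answers from 20 affected homes. The share, 28/140 = 20%, is right.

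**Item 3, share reporting later symptoms.** Use the same 100 homes, with truly new illness in 20%.

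- If no co-enrolled member's symptoms outlast the event, the share is 28/140 = 20%.
- If they always do, all 60 subjects in three-enrollee homes answer yes: (16 + 60) / 140 = 76/140 = 54%.
- Intermediate persistence falls between these two.

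With symptoms always persisting, the result runs from (18 + 20) / 110 = 35% when 10% of homes enrol two, to (14 + 90) / 160 = 65% when 30% enrol three.

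**The case against.** A reader might infer that the plan analyses the household items per subject and so overstates household illness. The documents do not support that. No household analysis is written at all: Section 6.3 names tract and hot spot or testing desert scores, and Section 6.2 rules out individual efficacy. The share of participants who report another ill member is also a legitimate descriptive quantity, and Section 2.1 does not say that a per-household share is wanted. The items are yes/no flags, not case counts. As the swapped-rate case shows, the direction of error for item 2 is not fixed. It could well reverse in homes where most members are already ill at entry and few are left to fall ill.

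A reader might also infer that co-enrolled patients are always counted as each other's onward cases. Items 1 and 2 already separate positives at the event from later ones, so a sibling positive at the event belongs in item 1. That answers the point for item 2 within one respondent's form. It neither links forms from the same home nor restricts item 3 to new onset.

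Nor can missed days simply be assumed to be triple-counted. The grid asks what the respondent's own illness caused, so two forms need not describe the same absence, though they may.

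Finally, co-enrolment may be uncommon. Every co-enrollee must be symptomatic within 48 hours, at least 5 years old, at least 20 kg and able to swallow tablets. Item 1 allows for shared attendance but says nothing about its frequency. Addresses are geocoded (Section 3.1), so later linkage may be possible, but the stated use is tract assignment and no household linkage is planned.

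What survives is narrower: records that cannot be grouped by home as the forms stand, and an item 3 that does not separate old illness from new.

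**Conclusion.** The point holds in this limited form and is a cheap improvement. Forms used as written allow one household event to appear as several unlinked yes answers, so counts and apparent precision could be inflated. Item 3 can record co-enrolled patients' continuing illness as household illness after the event. For item 2 the per-subject and per-household shares differ only if illness rates differ between single- and multi-enrollee homes, and the error can go either way. Missed days of household members may be repeated across forms.

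All percentages above rest on assumed enrolment patterns and illness rates. If every home enrolled one member, none of these effects would arise. The household data have no stated comparator, test or precision target, so no planned inference is overturned, and the tract comparison is untouched. The point goes beyond missing analysis detail because these are properties of the forms: an analysis rule written later could not separate new from continuing illness in item 3, and could group homes only by unplanned address matching.

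**What to change.** Leave entry, testing and treatment open to all household members. Then, before data collection:

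1. Add a household number to the case report form and the 14-day survey, or state that forms will be linked by the address already geocoded.
2. Name the first-enrolled member as the household's index, and record or analyse the household items, including household members' missed days, once per household.
3. Reword item 3 to ask about symptoms that began after the event in members who were neither enrolled nor already ill at the event.
4. State this unit of analysis in Section 2.1 or 6.5.

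The cost is one form field, one reworded question and a sentence or two of text. The drawback is a smaller denominator for the household measure: homes instead of subjects.
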